## 8.4.4 Reporting Serious Adverse Events

#### 8.4.4.1 REPORTING OF SERIOUS ADVERSE EVENTS TO SPONSOR

This section describes the responsibilities of the site investigator to report serious adverse events to the sponsor via the DCC eCRF. Timely reporting of adverse events is required by 21 CFR and ICH E6 guidelines.

Site investigators must report all serious adverse events (see Section 8.2.4, Serious Adverse Event), regardless of relationship or expectedness within 24 hours of discovering the event.

For serious adverse events, all requested information on the AE/SAE eCRF should be provided to the DCC. However, unavailable details of the event should not delay submission of the known information. As additional details become available, the AE/SAE eCRF should be updated and submitted.

#### 8.4.4.2 REPORTING OF ADVERSE EVENTS TO IRBS

All investigators must report adverse events in a timely fashion to their respective IRBs in accordance with applicable regulations and guidelines.

## 8.4.4.3 REPORTING PREGNANCY

Any pregnancy that occurs during a clinical study that is using an investigational drug must be reported to the DCC utilizing the SAE report form. This report is for tracking purposes only. The investigator will counsel the subject and discuss the risks of continuing with the pregnancy and the possible effects on the fetus, and will encourage the subject to discuss those choices with her obstetrician. All pregnancies that are identified during the study must be followed to conclusion and the outcome of each must be reported using the follow-up SAE report form. A woman who wishes to become pregnant while on the study will be counseled as to her choices and, if she decides to stop using contraception, will be dropped from the study.

# 8.5 Review of Safety Information

#### 8.5.1 Medical Monitor Review

The DAIT/NIAID and NIDDK Medical Monitors will receive monthly reports compiling new and accumulating information on AEs, SAEs, and pregnancies recorded by the sites on appropriate eCRFs.

In addition, the Medical Monitor will review and triage SAE and pregnancy reports received from the DCC.

## 8.5.2 **DSMB Review**

The Data and Safety Monitoring Board (DSMB) will review safety data yearly during planned DSMB Data Review Meetings. Data for the planned safety reviews will include, at a minimum, a listing of all reported AEs and SAEs.

## 9. MECHANISTIC ASSAYS

## 9.1 Metabolic Testing

## 9.1.1 Study Endpoints

Because the assessment of islet graft function is dependent on complex physiologic relationships between the graft and its recipient, no single test adequately addresses the viability of the transplant. The primary endpoint of duration of graft function addresses the clinically important outcome.

#### 9.1.1.1 GLYCEMIC CONTROL

Glycemic control will be assessed by HbA1c (%), which will be analyzed at the central laboratory.

## 9.1.1.2 HYPOGLYCEMIA

An episode of severe hypoglycemia is defined as an event with one of the following symptoms: memory loss; confusion; uncontrollable behavior; irrational behavior; unusual difficulty in awakening; suspected seizure; seizure; loss of consciousness; or visual symptoms, in which the subject was unable to treat him/herself and which was associated with either a blood glucose level <54 mg/dL (3.0 mmol/L) or prompt recovery after oral carbohydrate, IV glucose, or glucagon administration.

#### 9.1.1.3 MIXED-MEAL TOLERANCE TEST (MMTT)

Basal (fasting) and stimulated glucose and C-peptide levels will be determined using the MMTT. Subjects will be instructed not to eat or inject short-acting (or bolus) insulin after 8 PM the night before the test. Evening or bedtime administration of long-acting insulin will be permitted, as will consumption of water. Subjects receiving CSII (insulin "pump" therapy) may remain on the basal rate of insulin. Subjects will arrive fasting to the transplant or diabetes clinic where the capillary BG will be checked. If the BG is <70 mg/dl (3.89 mmol/L) or >180 mg/dl (10 mmol/L), the test will be rescheduled for the next possible day. If the BG is 70 – 180 mg/dl (3.89 – 10 mmol/L), basal glucose and c-peptide levels will be drawn. Immediately after, the subject will receive 6 mL per kg body weight (to a maximum of 360 mL) of Boost® High Protein Drink (or a nutritionally equivalent substitute) to consume in 5 minutes starting at time = 0. Then, at time = 60 minutes and time = 90 minutes, stimulated glucose and C-peptide levels will again be drawn.

Each blood sample collected for c-peptide and glucose determination will be drawn according to University of Washington (Seattle, WA) SOP and will be shipped frozen to U of W for measurement in the core laboratory.

## 9.2 Immunologic Testing

Although insulin independence can be achieved via transplantation of an adequate number of viable, functional islets, a gradual reduction in the percent insulin independent patients occurs over time, with approximately 25% of patients still insulin free at 4 years post-transplant. Immune mediated islet destruction in the form of allorejection and/or recurrent autoimmunity, as well as attrition of a marginal islet mass due to exhaustion and/or toxicity of immunosuppressive agents, have all been postulated to play a role in islet loss. In order to begin to dissect the role of immune mediated reactions in allograft loss, tests will be done to determine if sensitization to donor allo- or islet autoantigens has occurred. In addition, maintenance of protective immunity in the setting of immunosuppression will be addressed.

While methods for determination of allo- and autoantibody have been extensively studied and are fairly well-established, reliable, reproducible and validated methods for assessment of T cell immunoreactivity to allo and/or autoantigens do not exist. For the most part, these techniques are time-consuming, technically demanding and require large blood volumes and significant staff time for set up and analysis of the resultant data. Several methods are undergoing testing in multiple T1D consortia (*e.g.*, ELISPOT, tetramer staining, T cell proliferation assays) to determine which tests provide the most reliable data with regards to distinguishing between patients with T1D vs. normal controls (for autoantigen) and to improve techniques for assessing recipient anti-donor reactivity.

## 9.2.1 Immune Assays

#### 9.2.1.1 ALLOANTIBODY

Development of alloantibody is generally associated with longer term graft loss. Development of alloantibody specific for 1 or 2 HLA antigens can now be defined using assays that incorporate HLA specific monoclonal antibodies. Alloantibody assessments will be performed at each site's laboratory for subjects who experience graft failure during participation in CIT08 and subsequently discontinue immunosuppression.

#### 9.2.1.2 ARCHIVED SERUM

In order to ensure that we will ultimately gain as much information as possible from these trials, and due to the ongoing development of assays such as T cell assays, serum will be archived for future analyses. Details for subjects regarding the archiving of samples and use for future assays are contained in the study's informed consent form. Subjects will have the option of whether or not they want to have samples archived and will indicate their choice on the informed consent form. A subject's choice regarding archiving samples will not affect his/her participation in the study.

Serum: Blood will be collected to obtain serum and archived in the NIDDK repository.

## 10. STATISTICAL CONSIDERATIONS AND ANALYTICAL PLAN

## 10.1 Study Endpoint Assessment

## 10.1.1 Primary Endpoint

The primary endpoint is time to islet graft failure. The purpose of the analyses will be to estimate the probability of islet graft failure as a function of time from entry into the study . Life table methods will be used to estimate the survival curve and provide confidence intervals for the probability of islet graft survival for selected time points.

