## 4. STUDY DESIGN

This is an open-label, multi-center cohort study for participants from the CIT02, CIT03, CIT04, CIT05, CIT06, and CIT07 studies who continue to have islet graft function. These participants will continue immunosuppressive medications under CIT08 and will be assessed for islet function on an annual basis.

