# 4.1 Study Endpoints

## 4.1.1 **Primary Endpoint**

The primary endpoint is duration of sustained **islet allograft function** as determined by evidence from MMTT of c-peptide production at each anniversary of the final transplant. A c-peptide level greater than or equal to 0.3 ng/mL at 0, 60, or 90 minutes will be considered evidence of islet allograft function.

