# 7.2 Follow-up Visits

Subjects will be followed in this study after termination from the CIT parent study until the end date of the CIT08 study. Follow-up is comprised of quarterly visits done locally for safety monitoring and annual visits at the study center to assess graft function (if applicable) and safety.

Retrospective medical chart review will be conducted as needed to collect available follow-up information due to:

- delayed enrollment in CIT08 after termination from the CIT parent study
- the time period between termination from CIT08 prior to extension of the duration of follow-up and subsequent re-enrollment

This retrospective chart review will collect evidence of graft failure in addition to the follow-up assessments outlined in Appendix 1.

Subjects are allowed to concurrently enroll in and be screened for a non-CIT islet transplant study at any point during participation. Once study treatment in the non-CIT study is initiated, they will be withdrawn from CIT08 (see section 6.1).

Subjects with confirmed **graft failure** will not complete metabolic assessments. Subjects who experience graft failure and subsequently stop immunosuppression will have alloantibody assessed 3 months after their last dose of immunosuppression.

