## 10.1.2 Secondary Endpoints

Insulin usage will be estimated from the one-week self report values. Estimates of population means and confidence intervals for those means will be reported for each follow-up visit. Linear mixed models methods will be used to describe the profile of change with time.

Numbers of severe hypoglycemic events will be estimated from the self report values obtained at each follow-up visit. Estimates of population means and confidence intervals for those means will be reported for each follow-up visit. Linear mixed models methods with appropriate likelihood functions will be used to describe trends with time.

HbA1c and serum creatinine levels will be measured at central laboratories at study entry and at the annual follow-up visit. GFR will be estimated using the updated CKD-EPI method. Estimates of population means and confidence intervals for those means will be reported for each follow-up visit. Linear mixed models methods will be used to describe trends with time.

Incidence of serious adverse experiences will be tabulated by body system and MeDRA code.

Life table methods will be used to estimate mortality rates.

The overall incidence of alloantibody conversion will be reported as a rate per 100 days of follow-up. A 95% confidence interval for the rate will be computed using boot-strap methods.

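### CIT08 defines its primary endpoint by final-transplant anniversaries but times graft failure from an undefined study entry, and reports a single alloantibody test as a rate per 100 days

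*Protocol*

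**What the plan says.** CIT08 Section 4.1.1 and the CIT08 synopsis make duration of graft function the primary endpoint, "as determined by evidence from MMTT of c-peptide production at each anniversary of the final transplant". The CIT08 schedule of events (Appendix 1) also hangs its visits on the anniversary of the last islet transplant.

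CIT08 Section 10.1.1 restates the endpoint: "The primary endpoint is time to islet graft failure". The aim is to "estimate the probability of islet graft failure as a function of time from entry into the study", and the method is fixed: "Life table methods will be used to estimate the survival curve".

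Entry has no single meaning. The synopsis starts CIT08 follow-up after termination from the parent study. Section 7.1 enrols the subject once consent is obtained. Section 7.2 expects "delayed enrollment in CIT08 after termination from the CIT parent study" and also allows re-enrolment after an earlier termination, with chart review to fill the gaps. Section 7.3 adds another clock, placing annual visits around the anniversary of the last parent-study visit.

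For alloantibody, Section 4.1.2 defines the endpoint as presence after graft failure once immunosuppression is off. Section 7.2 says that subjects whose graft fails and who then stop immunosuppression "will have alloantibody assessed 3 months after their last dose of immunosuppression". Section 9.2.1.1 and Appendix 1 agree, and Appendix 1 schedules no baseline or annual sample. Section 10.1.2 nevertheless states: "The overall incidence of alloantibody conversion will be reported as a rate per 100 days of follow-up", with a bootstrap interval.

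**The concern.** Duration of function begins at transplant. A curve that begins at CIT08 entry estimates how much longer a graft lasts, given where it stood at entry. If entry comes at different graft ages, each point on the curve mixes grafts of different ages. Collecting long-term follow-up is CIT08's stated purpose, so its primary curve should estimate the quantity that its endpoint section defines.

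The alloantibody problem is separate. One yes/no test per eligible subject supports a proportion. Turning it into a rate requires a person-time denominator, and the protocol does not say whose days count. The word conversion also implies a known negative result beforehand. CIT08 takes no such sample and does not say that parent-study results will serve.

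**Working it through.** CIT08 gives no sample size, power or expected failure rate that depends on this point, so there is no figure of the plan's to reproduce.

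**1. Graft age at time zero, using CIT-05 as the example parent.** Inputs are CIT-05 activation in November 2006, 24-month accrual, follow-up to 12 months after the final transplant, no further transplant after 8 months from the first, and CIT08 activation in June 2011. Transplants are assumed to have kept to the accrual plan.

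- Only transplant in November 2006: the parent study ends in November 2007. The wait to June 2011 is 43 months, so the earliest enrolment is 43 + 12 = 55 months after transplant.
- First transplant in November 2008, final one 8 months later in July 2009: the earliest enrolment is 23 months after the final transplant.
- If entry means parent-study termination, or if a subject was accrued late, time zero is about 12 months after the final transplant.

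So time zero can lie between roughly 12 and 55 months within one parent trial, depending on the subject and on the meaning of entry. There are five other parent trials.

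**2. Does the clock change the answer, and in which direction?** This is an illustration, not a forecast. Take a Weibull curve S(t) = exp[−(λt)^k] with S(60 months) = 0.80. CIT-05 Section 1.5.4 gives 80% at 5 years as an upper figure. Failure within 36 months of entry at graft age e, given function at entry, is 1 − S(e + 36)/S(e). For k = 1, 60λ = −ln 0.80 = 0.223, so 36-month failure is 1 − exp(−0.223 × 36/60) = 12.5% on either clock.

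| Shape k | 36 months from transplant | Entry at 12 months | Entry at 23 months | Entry at 55 months |
|---|---|---|---|---|
| 0.6 (falling hazard) | 15.1% | 10.4% | 9.1% | 7.2% |
| 1.0 (constant) | 12.5% | 12.5% | 12.5% | 12.5% |
| 1.5 (rising) | 9.9% | 13.0% | 15.2% | 19.8% |

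At equal elapsed time the two clocks agree only under a constant hazard. The sign of the difference follows the hazard shape.

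**3. Alloantibody.** Assume 84% test positive. CIT-05 Section 1.5.1.3 reports about that proportion with raised panel-reactive antibody after graft loss and stopped immunosuppression. The rate per 100 days is 0.84 / D × 100, where D is the days counted per tested subject.

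- D = 90 (about the interval from last dose to test): 0.93
- D = 365: 0.23
- D = 2,222 (1 June 2011 to 1 July 2017, the longest possible CIT08 follow-up): 0.04

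The same results differ by a factor of 2,222 / 90, about 25, through the denominator alone. Adding the follow-up of untested subjects would lower the figure further.

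**The case against.** The strongest defence is that an entry clock is legitimate in an extension study and that Section 10.1.1 states its clock openly. Section 4.1.1 fixes when function is assessed and never says in so many words that time zero is the transplant. That is fair as far as it goes: survival from entry is a valid conditional estimate if labelled as one. It is still not the duration of function that the endpoint section defines, and it has no clear start while entry has two meanings.

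A reader might infer that the entry clock overstates durability. The documents do not support that as a general claim. The table above shows agreement under a constant hazard and the reverse under a rising one. Setting survival three years after entry against survival at the corresponding, older graft age compares different elapsed times and says nothing about the clock.

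A reader might also infer that the cohort consists only of survivors, since CIT08 Section 4 describes participants "who continue to have islet graft function". The inclusion criteria in Section 3.1 require only participation in a parent study, and Section 7.2 makes graft assessment conditional and has chart review look for graft failure. Selection on function is possible but not established. Nor do failures before enrolment necessarily lack a valid time: if entry means parent-study termination, they have one.

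On alloantibody, it is one reading, not a certainty, that untested person-time would be counted. That the denominator is undefined is certain.

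Finally, CIT08 is a single-arm descriptive study with no stopping rules and no stated hypothesis. That limits the consequences but does not remove the mismatch.

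**Conclusion.** Both points stand as errors in what the protocol fixes, not as detail left to an analysis plan. The primary curve as written estimates conditional residual function from an undefined entry that occurs at differing graft ages, whereas the endpoint is tied to the final transplant. The direction and size of the resulting difference cannot be established from the documents. The 12-to-55-month spread rests on CIT-05's planned dates and on which meaning of entry is used. The Weibull figures serve only to show that the sign is open.

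The alloantibody rate is not interpretable as written. Its value can move about 25-fold on the denominator, under the assumptions of 84% positive and 90 to 2,222 days. The data support a proportion.

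The impact is confined to the descriptive CIT08 follow-up. The CIT-05 primary endpoint, insulin independence at 75 days, is untouched.

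**What to change.** In CIT08 Section 10.1.1, set time zero at the final islet transplant. Use parent-study and chart-review data, with delayed entry (left truncation) for any period in which the subject was not observed. Moving the origin alone is not enough. If enrolment depended on a working graft, earlier time contributed only by those who later enrolled is failure-free by selection, and must be left-truncated or supplied by all parent-study recipients. Allow for failures that come to light only at an annual MMTT, since their dates are known only to within an interval.

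Define entry once, including for re-enrolled subjects. Label any entry-based curve as conditional survival. Reconcile the visit clocks in Section 7.3 and Appendix 1. They nearly coincide for a CIT-05 subject who finished on schedule at 12 months after the final transplant, but need not otherwise.

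In Section 10.1.2, replace the alloantibody rate with the number positive among those tested at three months and an exact binomial 95% confidence interval. If conversion is to be kept, say which parent-study sample supplies the negative baseline.

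The cost is wording in Sections 7.3, 10.1.1 and 10.1.2 and in the analysis plan. No visits or samples are added: the schedule already needs the final-transplant date, and the parent-study data are already held. With delayed entry, estimates at early graft ages may rest on few subjects, so numbers at risk should be shown.

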## 10.1.2 Secondary Endpoints

Insulin usage will be estimated from the one-week self report values. Estimates of population means and confidence intervals for those means will be reported for each follow-up visit. Linear mixed models methods will be used to describe the profile of change with time.

Numbers of severe hypoglycemic events will be estimated from the self report values obtained at each follow-up visit. Estimates of population means and confidence intervals for those means will be reported for each follow-up visit. Linear mixed models methods with appropriate likelihood functions will be used to describe trends with time.

HbA1c and serum creatinine levels will be measured at central laboratories at study entry and at the annual follow-up visit. GFR will be estimated using the updated CKD-EPI method. Estimates of population means and confidence intervals for those means will be reported for each follow-up visit. Linear mixed models methods will be used to describe trends with time.

Incidence of serious adverse experiences will be tabulated by body system and MeDRA code.

Life table methods will be used to estimate mortality rates.

The overall incidence of alloantibody conversion will be reported as a rate per 100 days of follow-up. A 95% confidence interval for the rate will be computed using boot-strap methods.

# 10.2 Patient and Demographic Data

## 10.2.1 Baseline Characteristics and Demographics

Summary descriptive statistics for baseline and demographic characteristics will be provided for all subjects in the ITT sample. Demographic data will include age, race, sex, body weight, and height; these data will be presented in the following manner:

- Continuous data (*i.e.*, age, body weight, and height) will be summarized descriptively by mean, standard deviation, median, and range.
- Categorical data (*i.e.*, sex and race) will be presented as enumerations and percentages.

Statistical presentation for baseline and demographic characteristics may be further summarized by values of important baseline predictors of outcome and will be further defined in the SAP.

# 10.3 Reporting Deviations from Original Statistical Plan

The principal features of the study design and of the plan for statistical analysis of the data are outlined in this protocol and in the subsequent SAP. Any changes in these principal features will require a protocol or an SAP amendment, which would be subject to review by the independent DSMB, the study sponsor, and the health authorities. These changes will be described in the final report as appropriate.

## 11. IDENTIFICATION AND ACCESS TO SOURCE DATA

## 11.1 Identifying Source Data

The investigator is required to keep accurate records to ensure that the conduct of the study is fully documented (see section 12). The results of all clinical and clinical laboratory evaluations will be maintained in the subject's medical records and the data will be transferred to clinical CRFs.

Safety data will be recorded on CRFs specifically designed for this purpose. All data will be reviewed periodically by the DSMB and IRB. The DSMB and/or the IRB have the authority to withdraw any subjects and/or terminate the study because of safety findings.

## 11.2 Permitting Access to Source Data

The investigational site participating in this study will maintain the highest degree of confidentiality permitted for the clinical and research information obtained from the subjects in this clinical trial. Medical and research records should be maintained at each site in the strictest confidence. However, as a part of the quality assurance and legal responsibilities of an investigation, the investigational site must permit authorized representatives of the sponsor(s), including pharmaceutical collaborators and their commercial partners, and health authorities to examine (and when required by applicable law, to copy) clinical records for the purpose of quality assurance reviews, audits, and evaluations of the study safety and progress. Unless required by the laws that permit copying of records, only the coded identity associated with documents or with other subject data may be copied (and all personally identifying information must be obscured). Authorized representatives as noted above are bound to maintain the strict confidentiality of medical and research information that is linked to identified individuals. The investigational site will normally be notified before auditing visits occur.

